**Data Quality and Management:**

[name] will supervise and train the Research Assistant and all key personnel on study procedures to ensure that all procedures are followed and are in compliance with the approved Yale University IRB protocol. [name] will also provide training and oversight to study staff to ensure data are generated, documented, and reported according to requirements by the Yale University IRB and the funding source. The Biostatistician, [name], will also oversee quality assurance of data.

d. For multi-site studies for which the Yale PI serves as the lead investigator:

- i. How will adverse events and unanticipated problems involving risks to subjects or others be reported, reviewed and managed? *Write here*
- ii. What provisions are in place for management of interim results? *Write here*
- iii. What will the multi-site process be for protocol modifications? *Write here*

12. **Statistical Considerations:** Describe the statistical analyses that support the study design.

*Write here*

**Aim 1: Evaluate the feasibility, acceptability, and helpfulness of the real-time smoking intervention.** We will use descriptive statistics to summarize participant ratings of satisfaction and perceived usefulness of the intervention at the end of treatment, including characterizing adherence and feasibility of using the smartband device based on self-report and objective adherence (i.e., number of days wearing the smartband).

**Aim 2: Assess the preliminary efficacy of the real-time intervention as an adjunct to standard tobacco treatment.** We will compare biochemically confirmed 7-day point prevalence abstinence at the end of treatment (i.e., reported abstinence from cigarettes during the last week of the study that is confirmed with  $CO \leq 4 \text{ ppm}$ ) to estimate effect sizes for ST+ vs. ST. We will also compare continuous outcome measures between ST+ and ST that are proximal indices of good clinical response: number of days abstinent and changes in cigarettes per smoking day from baseline to week 8. We will use independent sample t-tests to compare total days abstinent between ST+ and ST and a 2x2 mixed ANOVA (time x condition) to compare changes in cigarettes per smoking day from baseline to week 8.

**Sample Size Justification & Power Calculation:** This study is a developmental project testing the feasibility and potential efficacy of adding a novel intervention to enhance standard smoking cessation treatment. Sample size for the current study is based on guidelines for Stage 1 treatment development studies that suggest a minimum of 15 participants per experimental arm to obtain a reliable effect size estimate. Our target sample (25 per group) is sufficient to determine preliminary efficacy and estimate effect sizes for the binary cessation outcome, 7-day point prevalence abstinence at the end of treatment. This sample size produces two-sided 95% confidence intervals for the difference in population proportions with a half-width that is equal to 22%-24% when the difference in abstinence rates between groups (ST+ vs. ST) in estimated sample proportions is 10%-15% (e.g., 25% vs. 15%, 30% vs. 15%,

HIC# 2000024740

35% vs. 20%). For the continuous smoking outcomes, based on power=.80 and two-tailed alpha=.05, we can detect a statistically significant difference between groups of 4 days abstinent (SD=5) and a difference of 6 cigarettes per smoking day (SD=8) between baseline and end of treatment by group.

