## SECTION I: RESEARCH PLAN

1. **Statement of Purpose:** State the scientific aim(s) of the study, or the hypotheses to be tested.

The proposed project will use wearable technology to test the feasibility and efficacy of delivering a novel real-time smoking intervention to improve standard tobacco treatment. 50 adult daily smokers will be recruited from an outpatient tobacco treatment center to participate in an 8-week pilot intervention. Participants will be randomly assigned to a control group (standard treatment ST, n=25) or experimental group (standard treatment plus real-time smoking intervention ST+, n=25). The control group (ST) will not receive real-time feedback about their smoking. The experimental group (ST+) will receive real-time feedback as soon as smoking is detected using wearable technology during the 8-week intervention. Specific aims include:

**Aim 1: Evaluate the feasibility, acceptability, and helpfulness of the real-time smoking intervention.** We will characterize rates of adherence (i.e., number of days wearing the smartband) and evaluate participant satisfaction and perceived usefulness of the intervention using post-treatment interviews and ratings.

**Aim 2: Assess the preliminary efficacy of the real-time intervention as an adjunct to standard tobacco treatment.** We will compare biochemically confirmed 7-day point prevalence abstinence at the end of treatment (week 8) to estimate effect sizes for ST+ vs. ST. Additional outcomes will compare total number of days abstinent and changes in cigarettes per smoking day from baseline to end of treatment between ST+ and ST as proximal indices of good clinical response that are related to long-term cessation outcomes.

2. **Probable Duration of Project:** State the expected duration of the project, including all follow-up and data analysis activities.

2 years. We anticipate recruiting and enrolling 50 subjects over 20 months and will complete data entry and analysis by the end of 2 years.

3. **Background:** Describe the background information that led to the plan for this project. Provide references to support the expectation of obtaining useful scientific data.

[figure not shown]

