**Overview:** The proposed study will evaluate the feasibility and efficacy of a real-time smoking intervention as an adjunct to enhance standard tobacco treatment. 50 adult smokers will be randomly assigned to a control group (standard tobacco treatment, ST, n=25) vs. an experimental group (standard treatment plus a real-time smoking intervention, ST+, n=25). Randomization to group (1:1) will be stratified by average number of cigarettes smoked per day at baseline (< or ≥ 10 cigarettes per day) to balance groups on smoking intensity. Enrolled participants will complete research visits at 4 weeks and 8 weeks (see Figure 1). Participants will receive financial compensation for their time spent completing research activities: \$20 for each appointment (week 0,4,8) for a total of \$60. Participants will earn a \$20 bonus for attending the last visit (week 8) and returning the smartband and charger. These visits will take place remotely in which the participant will speak with our research staff by phone or video call, at the tobacco clinic, at our research office, or at a location that is convenient, such as a public place.

**Recruitment:** We will recruit from the Yale Tobacco Treatment Service (TTS) and the Winchester chest clinic. These programs are a specialized outpatient services at Yale-New Haven Hospital that provides individual tobacco treatment to a large patient

population of current smokers. New patients referred to the TTS and Winchester chest clinic will be informed about the study and will be invited to set up a screening appointment if interested. To facilitate participant enrollment and retention, study procedures may take place in person or remotely (e.g., phone, secure video conference) when possible.

Screening Assessments: To screen for eligibility, participants will complete the following assessments including: 1) Smoking history to assess smoking quantity and frequency such as number of cigarettes per day and number of years smoked, 2) self-reported other tobacco and drug use for the past 30 days. Participants may also complete biochemical verification of smoking status, such as breath carbon monoxide (CO) measured in parts per million or cotinine measured in a small sample of urine or saliva.

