Approach-Avoidance Task (AAT) (week 0, 4, 8): An objective behavioral task that measures the tendency to automatically approach smoking stimuli (e.g., cigarettes). Our research team has used an adapted version of the approach-avoidance task (AAT) to measure smoking approach and avoidance action tendencies. The task starts with 20 practice trials in which participants learn to push or pull the joystick in response to picture format (landscape or portrait). The practice phase is followed by 160 test trials in which pictures of cigarette stimuli (e.g., cigarettes, cigarette packages) and non-cigarette stimuli (e.g., pencil) come equally in

push- or pull-format (this takes 5 to 10 minutes). Picture format (landscape or portrait) to response assignment (push or pull) is counterbalanced, with half the participants pulling landscape pictures and half portrait pictures. The smoking approach bias represents the relative difference between pushing and pulling the joystick in response to the smoking stimuli, measured as mean reaction time. Evidence supports reliable approach tendencies related to substance use and indicates that meaningful changes in automatic approach tendencies related to substance use outcomes can be detected after one week.

End of Treatment Ratings (week 8): We will evaluate participant satisfaction and perceived usefulness of the treatment across both conditions with post-treatment interviews and ratings.

Analytical Plan:

Data Management and Statistical Analyses: The proposed study will follow HIPAA guidelines for data collection, management, and monitoring. Data analyses will use the intention-to-treat (ITT) principle, where missing data will be treated as smoking. Data analyses will be conducted under the supervision of [name] who is a biostatistician. Data on quantitative outcomes will be examined for conformity to the normal distribution and transformation or non-parametric methods will be used if necessary.

Aim 1: Evaluate the feasibility, acceptability, and helpfulness of the real-time smoking intervention. We will use descriptive statistics to summarize participant ratings of satisfaction and perceived usefulness of the intervention at the end of treatment, including characterizing adherence and feasibility of using the smartband device based on self-report and objective adherence (i.e., number of days wearing the smartband).

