#### Safety and Study Progress Reviews:

[name] will lead a weekly research meeting with key personnel to review the status of all enrolled participants and discuss the eligibility of potential participants. At this weekly meeting, [name] will review study progress (i.e., recruitment goals, retention, protocol adherence). Any adverse events will be reviewed at this meeting, including serious adverse events that may have been attended to outside of this weekly meeting. An annual progress

report will be submitted to Yale University IRB and the funding agency that lists and summarizes adverse events, documents whether adverse event rates are consistent with pre-study assumptions, summarizes recruitment and retention and reason for dropouts, and summarizes study progress related to the stated aims.

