**SECTION III: RECRUITMENT/CONSENT AND ASSENT PROCEDURES**

**1. Targeted Enrollment: Give the number of subjects:**

- Targeted for enrollment at Yale for this protocol: **50 adults**
- If this is a multi-site study, give the total number of subjects targeted across all sites: N/A

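### The .80 power stated for the two continuous outcomes uses all 25 enrolled per group with no attrition allowance, and the cigarettes figure falls short of .80 even with complete data if SD 8 is the SD of change

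*Combined protocol and SAP*

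**What the plan says.** Section I, item 12, Sample Size Justification & Power Calculation, rests the sample size on a Stage 1 guideline of at least 15 per arm. It then gives confidence-interval half-widths for the binary abstinence outcome ("Our target sample (25 per group) is sufficient to determine preliminary efficacy"). For the continuous outcomes it adds a power claim: "based on power=.80 and two-tailed alpha=.05, we can detect a statistically significant difference between groups of 4 days abstinent (SD=5", together with a difference of 6 cigarettes per smoking day with SD 8.

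The 25 per group is the whole enrolment. Section I, item 2, says "We anticipate recruiting and enrolling 50 subjects over 20 months". Item 4 allocates 1:1, and Section III, item 1, gives the same target of 50 adults. No dropout rate, inflation or over-enrolment is stated.

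The plan does provide for loss of data. The Analytical Plan in item 4 adopts intention to treat, "where missing data will be treated as smoking". The annual progress report described in item 11 "summarizes recruitment and retention and reason for dropouts". The planned tests are a two-sample t-test for total days abstinent and a 2x2 mixed ANOVA (time by condition) for cigarettes per smoking day.

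**The concern.** The analysis section plans for missing data and the power statement does not. The missing-data rule also acts differently on the two outcomes.

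- **Days abstinent.** A dropout stays in the analysis and the unobserved days become smoking days. The number analysed stays at 25 per group, but the difference between arms shrinks and the spread of the outcome may change.
- **Cigarettes per smoking day.** Calling a missing week-8 visit smoking supplies no cigarette count. Unless some other rule provides one, that participant cannot enter the ANOVA and the number analysed falls below 25.

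Both outcomes will be formally tested under Aim 2. A null result would be read against a claimed 80% power that the planned analysis may not have.

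**Working it through.** **Inputs from the documents.** Two-sided alpha .05; 25 per group; difference 4, SD 5 (standardised 0.80); difference 6, SD 8 (0.75 if SD 8 is the SD of change). The time-by-condition test in a 2x2 mixed ANOVA is equivalent to a t-test on change scores.

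**Formulas.** Normal approximation: power = Φ(d√(n/2) − 1.96). Exact: noncentral t with 2n − 2 degrees of freedom and noncentrality d√(n/2).

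**Step 1: reproduce the 4-day figure.** 0.80 × √12.5 = 2.828, and Φ(2.828 − 1.960) = 0.807. Noncentral t with 48 df gives 0.791. The detectable difference at .80 is 3.96 (normal) or 4.04 (t). The stated figure reproduces, with no margin: 25 per group are needed by the normal formula and 26 by t. At 24 per group power is 0.791 (normal) or 0.774 (t).

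**Step 2: check the 6-cigarette figure with complete data.** 0.75 × √12.5 = 2.652, and Φ(2.652 − 1.960) = 0.755. Noncentral t gives 0.738. The detectable difference at .80 is 6.34 (normal) or 6.47 (t), and 28 or 29 per group would be needed for 6. A one-sided test gives 0.843 or 0.834, which does not match .80 either. The figure could be recovered if SD 8 is a per-visit SD. The SD of change is then 8√(2(1 − ρ)), and 6 is detectable (t) when the baseline-to-week-8 correlation ρ is about 0.57 or more. No correlation is stated.

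**Step 3: days abstinent under missing = smoking, 25 per group.** The documents give no dropout rate or arm means, so the following are assumptions: equal random dropout in both arms; complete-data outcomes normal with SD 5 and difference 4; control mean 4, 8 or 12 days; dropouts credited with a fraction c = 0 or 0.4 of their abstinent days. For dropout proportion p and arm mean μ:

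- mean after the rule = μ(1 − p + pc)
- variance after the rule = (1 − p + pc²)(25 + μ²) − [μ(1 − p + pc)]²

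Example with p = 0.20, c = 0 and control mean 8. The means become 6.4 and 9.6, so the difference is 3.2. The variances are 0.8 × 89 − 6.4² = 30.24 and 0.8 × 169 − 9.6² = 43.04. The pooled SD is √36.64 = 6.05, and power is 0.45.

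Results at 20% dropout (simulation of 40,000 trials agrees within about 0.01):

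| Control mean (days) | Credit | Difference | Pooled SD | Power |
|---|---|---|---|---|
| 4 | 0% | 3.20 | 5.14 | 0.58 |
| 4 | 40% | 3.52 | 4.81 | 0.72 |
| 8 | 0% | 3.20 | 6.05 | 0.45 |
| 8 | 40% | 3.52 | 5.18 | 0.65 |
| 12 | 0% | 3.20 | 7.21 | 0.34 |
| 12 | 40% | 3.52 | 5.69 | 0.57 |

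The SD widens in five of the six cases and narrows in one. With control mean 8, power at 10% dropout is about 0.60 (no credit) or 0.72 (40% credit). At 30% it is about 0.34 or 0.60.

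**Step 4: cigarettes per smoking day with loss.** If participants without a week-8 count leave the analysis, an assumed 20% loss leaves 20 per group. With SD 8 as the SD of change, power for 6 cigarettes is 0.637 (t) and the detectable difference is 7.27.

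**The case against.** Four objections deserve weight.

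- **The 4-day figure is calculated correctly, and its inputs are not labelled.** The plan does not say whether 4 days and SD 5 are complete-data values or values after missing days are counted as smoking. If they already describe the intention-to-treat outcome, 25 per group is right and dropout does not upset the statement. This stands: the dilution in Step 3 is conditional.
- **The size of the loss rests on assumed inputs.** No dropout rate is forecast, and listing dropouts as a reporting item is not a forecast. Zero credit is severe, because the timeline follow-back is also taken at week 4. A normal outcome with mean 4 and SD 5 puts about 21% of controls below zero days. This also stands, so the figures are a range and not an estimate.
- **The sample size was not derived from this power.** The 15-per-arm guideline is still met after 40% loss (25 × 0.6 = 15). The binary interval keeps 25 per group under missing = smoking, and its half-widths reproduce (22.0%, 22.8% and 24.4% against the stated 22%-24%). A reader might infer that the trial is too small or should enrol more. The documents do not support that.
- **A reader might infer that both detectable differences hold only with zero dropout.** That does not fit either outcome as documented. The 6-cigarette figure already falls short at zero dropout if SD 8 is the SD of change. The 4-day figure could survive dropout if its inputs are post-imputation values.

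What remains is that the plan claims .80 power without stating the follow-up it assumes, and that one of its two figures does not reproduce on the plain reading of its SD.

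**Conclusion.** The point holds in a limited form. For days abstinent it is an unstated assumption and not a calculation error: every enrolled participant is used and no margin is left. If the inputs are complete-data values, power under the plan's own rule is materially below .80 in every scenario examined. For cigarettes per smoking day there is a numerical shortfall before any dropout, conditional on SD 8 being the SD of change, and loss of week-8 counts adds to it. Neither result touches the abstinence outcome or the justification for 50 participants. Restating the paragraph before analysis is worthwhile because it corrects how a null result on these two outcomes would be read.

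**What to change.** Keep 50 participants and restate the power sentence in Section I, item 12.

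- **Days abstinent.** Say whether 4 days and SD 5 are complete-data values or values after missing days are counted as smoking. If complete-data, say that .80 needs complete follow-up. Then give the power at 25 per group after the missing-as-smoking rule, over a stated range of dropout, arm means and credited days. A completers-only figure should not be used here, because the planned analysis keeps dropouts in.
- **Cigarettes per smoking day.** Correct the complete-data detectable difference to about 6.5 (t; 6.3 by normal approximation), or state the SD and correlation that justify 6. Say how a missing week-8 count is handled. If those participants leave the analysis, give the detectable difference at the expected number with data, for example about 7.3 at 20 per group.

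The cost is a few sentences and less favourable stated figures. No participants, visits or procedures are added.

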**SECTION II: RESEARCH INVOLVING DRUGS, BIOLOGICS, RADIOTRACERS, PLACEBOS AND DEVICES**

*If this section (or one of its parts, A or B) is not applicable, check off N/A and delete the rest of the section.*

A. RADIOTRACE RS	 N/A
B. DRUGS/BIOL OGICS	 N/A
C. DEVICES	 N/A

**SECTION III: RECRUITMENT/CONSENT AND ASSENT PROCEDURES**

**1. Targeted Enrollment: Give the number of subjects:**

- Targeted for enrollment at Yale for this protocol: **50 adults**
- If this is a multi-site study, give the total number of subjects targeted across all sites: N/A

**2. Indicate recruitment methods below. Attach copies of any recruitment materials that will be used.**

 Flyers	 Internet/web postings	 Radio
 Posters	 Mass email solicitation	 Telephone
 Letter	 Departmental/Center website	 Television
 Medical record review*	 Departmental/Center research boards	 Newspaper
 Departmental/Center newsletters	 Web-based clinical trial registries	 Clinicaltrials.gov
 YCCI Recruitment database	 Social Media (Twitter/Facebook):	
 Other: Referral from Yale TTS		

\* Requests for medical records should be made through JDAT as described at

<http://medicine.yale.edu/ycci/oncore/availableservices/datarequests/datarequests.aspx>

**3. Recruitment Procedures:**

- Describe how potential subjects will be identified. We will recruit individuals from the Yale Tobacco Treatment Service (TTS) and the Winchester chest clinic. Yale TTS is a specialized outpatient service at Yale-New Haven Hospital that provides individual tobacco treatment to a large patient population of current smokers. New patients referred to the TTS or Winchester will be informed about the research study by their clinician or the administrative staff who schedules their appointments. Interested patients will provide verbal consent to be contacted by research staff.
- Describe how potential subjects are contacted. Research staff will first contact interested participants by phone to complete initial screening. If participants meet initial eligibility criteria, they will be scheduled for an intake visit. At the start of the intake visit, consent to participate will be obtained from all participants after the research procedures and risks associated with participation have been explained.
- Who is recruiting potential subjects? The PI and research staff will recruit potential subjects.

**4. Assessment of Current Health Provider Relationship for HIPAA Consideration:**

Does the Investigator or any member of the research team have a direct existing clinical relationship with any potential subject?

Yes, all subjects

Yes, some of the subjects

No

If yes, describe the nature of this relationship. We will recruit patients who are receiving tobacco treatment from the Yale TTS service and the Winchester chest clinic so we will be collaborating with their clinical providers (e.g., APRN tobacco treatment specialists, clinical pharmacists) and the administrative staff who schedules appointments and manages referrals for tobacco treatment. The tobacco treatment providers will be providing clinical services to each patient in addition to being part of the research team. Participation in the study is completely voluntary and does not impact the patient relationships with the tobacco counselors or their other healthcare providers. This is outlined in detail in the consent form.

**5. Request for waiver of HIPAA authorization:** (When requesting a waiver of HIPAA Authorization for either the entire study, or for recruitment purposes only. Note: if you are collecting PHI as part of a phone or email screen, you must request a HIPAA waiver for recruitment purposes.)

**Choose one:**

For entire study

For recruitment/screening purposes only

For inclusion of non-English speaking subject if short form is being used and there is no translated HIPAA research authorization form available on the University's HIPAA website at [hipaa.yale.edu](http://hipaa.yale.edu).

- i. Describe why it would be impracticable to obtain the subject's authorization for use/disclosure of this data: *Write here*
- ii. If requesting a waiver of **signed** authorization, describe why it would be impracticable to obtain the subject's signed authorization for use/disclosure of this data: **We request a waiver of signed authorization only for initial participant recruitment/screening purposes to obtain interested participants' phone numbers and/or email for voice and text communication to make initial contact with the research team. At the first phone contact with the research team, participants will provide verbal consent for the screening process. If participants prefer to complete the online screener through the Yale Qualtrics system, participants will indicate their consent to be screened by answering questions in the online screening survey.**

The investigator assures that the protected health information for which a Waiver of Authorization has been requested will not be reused or disclosed to any person or entity other than those listed in this application, except as required by law, for authorized oversight of this research study, or as specifically approved for use in another study by an IRB.

*Researchers are reminded that unauthorized disclosures of PHI to individuals outside of the Yale HIPAA-Covered entity must be accounted for in the "accounting for disclosures log", by subject name, purpose, date, recipients, and a description of information provided. Logs are to be forwarded to the Deputy HIPAA Privacy Officer.*

6. **Process of Consent/Accent:** Describe the setting and conditions under which consent/assent will be obtained, including parental permission or surrogate permission and the steps taken to ensure subjects' independent decision-making.

The entire consent form will be reviewed in detail with the participant in a private, one-on-one setting with a research staff member. The consent form will provide clear and explicit language about the smoking intervention components, smoking-monitoring procedures, and smartband use. Any questions the participant may have will be addressed. If participants wish, they may take the consent form home and consider it further before signing. They may also request to speak to anyone on the research team about questions they have or to consult others, including their physician and family members. Participants will sign 2 copies of the consent, retain one, and the researchers will keep the second copy on file. Participants will be informed that they are free to decline participation and withdraw from the study at any time and that neither action will adversely affect their relationship with any study personnel. Following resolution of any questions, the participant will be asked to sign the consent form, if he/she agrees to participate. For remote intake visits, the approved informed consent form will be provided online via Qualtrics to subjects in advance of participation. Research staff will review the consent form by phone or video conference with the potential participant, and research staff will answer any questions regarding the study or consent form at this time. Subjects who wish to participate will click "I accept" and electronically sign the document by initialing the Qualtrics form. A copy of the consent form will be automatically emailed to the participant.

7. **Evaluation of Subject(s) Capacity to Provide Informed Consent/Accent:** Indicate how the personnel obtaining consent will assess the potential subject's ability and capacity to consent to the research being proposed.

We will not be enrolling participants with limited decision-making capacity. We plan to exclude individuals with current serious psychiatric or medical illnesses. During the consenting process, the research assistant will read and review the consent form with the prospective participant. The research assistant will then ask the potential participant various questions about the consent form and study protocol to ensure the prospective participant sufficiently understands the study and the nature of their consent to participate.

8. **Non-English Speaking Subjects:** Explain provisions in place to ensure comprehension for research involving non-English speaking subjects. If enrollment of these subjects is anticipated, translated copies of all consent materials must be submitted for approval prior to use.

N/A

As a limited alternative to the above requirement, will you use the short form\* for consenting process if you unexpectedly encounter a non-English speaking individual interested in study participation and the translation of the long form is not possible prior to intended enrollment? YES  NO

**Note\*** If more than 2 study participants are enrolled using a short form translated into the same language, then the full consent form should be translated into that language for use the next time a subject speaking that language is to be enrolled.

Several translated short form templates are available on the HRPP website ([yale.edu/hrpp](http://yale.edu/hrpp)) and translated HIPAA Research Authorization Forms are available on the HIPAA website ([hipaa.yale.edu](http://hipaa.yale.edu)). If the translation of the short form is not available on our website, then the translated short form needs to be submitted to the IRB office for approval via modification prior to enrolling the subject. ***Please review the guidance and presentation on use of the short form available on the HRPP website.***

If using a short form without a translated HIPAA Research Authorization Form, please request a HIPAA waiver in the section above.

HIC# 2000024740

9. Consent Waiver: In certain circumstances, the HIC may grant a waiver of signed consent, or a full waiver of consent, depending on the study. If you will request either a waiver of consent, or a waiver of signed consent for this study, complete the appropriate section below.

Not Requesting any consent waivers

Requesting a waiver of signed consent:

- Recruitment/Screening only** (if for recruitment, the questions in the box below will apply to recruitment activities only)
- Entire Study** (Note that an information sheet may be required.)

For a waiver of signed consent, address the following:

- Would the signed consent form be the only record linking the subject and the research? YES  NO
- Does a breach of confidentiality constitute the principal risk to subjects? YES  NO

OR

- Does the research pose greater than minimal risk? YES  NO
- Does the research include any activities that would require signed consent in a non-research context? YES  NO

Requesting a waiver of consent:

- Recruitment/Screening only** (if for recruitment, the questions in the box below will apply to recruitment activities only)
- Entire Study**

For a full waiver of consent, please address all of the following:

